For Aim 2, all research data will be organized and managed using REDCap electronic data capture tools hosted at Northwestern University. REDCap (Research Electronic Data Capture) is a research management tool which enables a secure study website accessible to all IRB approved research team members regardless of study site. The REDCap website will be used to administer the screening, sociodemographics, baseline and follow-up questionnaires, and to organize medical record review data. My Guide usage data and weekly questionnaires will be captured via the CBITs My Guide interface and uploaded to REDCap to centralize all research information. Once collected, all research data will be imported into SPSS for cleaning and analysis. (The REDCap platform provides automated export procedures for seamless data downloads to common statistical packages.)

All data collected from participants will be kept strictly confidential, except as mandated by law. All research files, including study data, are kept on secure, password protected departmental and medical school servers. All electronic data will be stored on secure servers behind firewalls meeting all security requirements of the medical school.

For Aim 1c and Aim 2, all procedures regarding self-reported and EMR recorded data remain the same as were described above. Regarding confidentiality of information collected and transmitted via the smartphone application in Aim 1c and Aim 2 of the study, all data collected will be transmitted using Transport Layer Security (TLS) encryption to prevent eavesdropping and tampering of information and data while they are in the transmission pipeline. To prevent unauthorized access to the Smartphone, all phones will be set up to be password protected (password selected by the participant at

the time of phone training). All electronic data will be stored on secure servers behind firewalls at the Center for Behavioral Intervention Technologies at the Northwestern University Feinberg School of Medicine. Internet interventions and mobile assessments will be conducted through *Purple Development Environment*, which is a development and deployment platform created and maintained by the Northwestern University Center for Behavioral Intervention Technologies (CBITs). This platform uses up to date security measures that are consistent with those used by Electronic Medical Records and are HIPAA compliant. All data collected via the interventions and assessments are transmitted using Transport Layer Security (TLS) encryption to prevent eavesdropping and tampering information while it is in the transmission pipeline. In addition, all data stored within the intervention is de-identified with a unique key. Security measures to protect privacy threats associated with users' computers and devices include the following measures: users are automatically logged off of intervention and assessment tools after 5 minutes of no activity; any data stored locally is automatically encrypted using 128-bit Blowfish encryption based on the user authentication information and cannot be accessed without this information. (After five failed attempts to access, this information is deleted and must be restored from remote backup). All information collected by this application will be immediately transmitted to CBITs, this application does not save any data to the phone's memory.

During Aim 1c and Aim 2, each participant will login to the application with a unique password using an email address. Besides the email required for login, no other PHI will be collected by this application, or stored/requested by the application at any point. The FACT-G7, already administered to patients during the phone eligibility screening, will be re-administered weekly by the application, however note that the FACT-G7, a multiple choice questionnaire, does not collect any PHI. Application usage (e.g., number of logins to the application) will also be collected by the application.

Participants will be given the option to either use their own phone to download the application, or they can choose to borrow a study phone (an Android Nexus 5X) with the application already downloaded. Once the participant downloads the application or is provided with a study phone, we will create a unique account with the participant. Only an email address and password is required to register, if the participant does not have an email address, we will create a temporary email address using pseudonyms, which will be deleted at the end of the trial.

At the end of participation, the application will be deleted from the participant's phone, and no other information will be collected, unless the participant explicitly requests to continue using the application. Participants that elect to continue using the phone, will be instructed to not complete a weekly questionnaire. For participants that borrowed a study phone, the application will also be deleted from the phone, and the phone will be reset to the factory setting.

The master key with unique identifiers used to track the data collected during the application (the list with the unique application identifier and the email address) will be stored on a password protected server at Northwestern Feinberg School of Medicine and destroyed at the end of data collection by deleting it from the server. Only IRB approved members of the research staff will have access to the master key. The Northwestern site PI and a trained, bilingual research assistant will conduct the interviews in Aim 1a. The interviews for Aim 1a will be audio-recorded and transcribed resulting in a more complete data set than if only notes were taken of the responses. Audio recording for Aim 1a interviews is mandatory for the study as all recordings will be transcribed and analyzed for thematic content. Participants will not have the opportunity to edit the recordings or the transcripts. The audio tapes from Aim 1a will be reviewed by the Northwestern PI. In order to facilitate confidentiality, the patient's name will not be mentioned during the interview. The interviews will

be transcribed by GMR Transcription (a company used by many departments at Northwestern that already has an NU business associate agreement in place to work with study data). Five to 10% of the taped interviews will be chosen at random and their transcriptions checked for accuracy by the Northwestern PI or a trained research assistant working with the Northwestern PI. A code book will be developed to categorize the responses to the open-ended questions from the interviews.

Planned Analyses Aim 1: Grounded theory methods will be used to guide analyses for Specific Aim 1a. Grounded theory is appropriate when the study of social experiences aims to explain a process. Recordings from the interviews will be transcribed verbatim. All data will be coded using NVivo software. Responses from the interviews will be examined systematically. Based on the principles of grounded theory, two independent raters will generate a list of themes expressed by participants. Members of the study team will participate in an iterative group process to develop a coding manual used to identify themes from the interviews. We will reduce subjectivity by using two coders and a calculated agreement between coders (Kappa). The codes will then be compiled in frequency tables. For qualitative data analysis, an analogue to statistical power is “data saturation,” or the point at which successive information serves only to replicate previous content themes and no new information is obtained. Based upon recommended methods for determining saturation, we will consider a concept as “saturated” when it has been mentioned by at least 70% of the sample. Past research reveals that saturation often occurs within the first ten to twelve interviews and basic elements for themes are sometimes present as early as six interviews. We therefore expect to achieve data saturation with our proposed sample of 20 women. Analyses from Aim 1b include descriptive statistics on the USE Questionnaire and qualitative summaries of participants’ comments regarding the usability of the Smartphone-based application. Information obtained from participants in Aim 1b will be reviewed by the PI and Co-Investigator and based on these data they will make decisions to modify the Smartphone-based application, Mi Guia. Analyses for Aim 1c include descriptive statistics on the Smartphone-based application, Mi Guia (e.g., number of logins to the application, mean time spent on the application). These descriptive statistics will provide valuable information to the investigators as to how often participants are engaging with the mobile application and therefore using the intervention.

Planned Analyses Aim 2: Descriptive statistics will be used to characterize the overall sample and each condition. We will use Chi-square, Fisher’s exact tests, and Mann-Whitney U test for nonnormal data, as appropriate, to preliminarily examine differences in feasibility between the study conditions. While the sample sizes of 40 per condition will have 80% power to detect 0.63 standard deviations for our main outcomes. For all outcomes, change from baseline will be calculated and the mean changes within study condition will be converted to effect sizes. Effect sizes will be defined as the difference in means or proportions between the study conditions divided by the standard deviation of the outcome. Follow-up scores on the outcomes, HRQoL and cancer-specific distress, as well as all intervention targets, will be compared between study conditions, adjusted for baseline score, using analysis of covariance (ANCOVA). We will also reference established cutoffs for clinically meaningful differences for scores on the FACT, and FACT subscales, to identify ranges and patterns of change scores in HRQoL across the study conditions from study baseline to the follow-up assessments. Mixed effects models will be used to model the study outcome scores, and all intervention targets, over time for each group. Type of treatment, time since completion of active treatment, stage of diagnosis, education, marital status, language, comorbidities and age at diagnosis will be examined for their associations with study outcomes for potential entry as covariates in the statistical model.

14.0 Data Monitoring Plan to Ensure the Safety of Participants:

For Aim 1a and 1b the informed consents, all assessment measures and intervention modules will be reviewed and subject to approval by the Institutional Review Board at NU. As detailed in the Human Subjects section of the protocol and in the informed consent document, this study involves minimal risk to study participants. Regarding participant safety, any occurrence of a serious adverse event (e.g., hospitalization, injury, death) will be discussed at the weekly project meeting. Adverse events will be documented, logged, and submitted to the IRB within the mandated time frame. The PI will review the data safety quarterly, and a cumulative report will be submitted to the IRB on an annual basis as required for continuing review and/or final report. Interim analyses for the purposes of discontinuing the study will only be conducted if during a review of adverse events it seems that risks or complications appear to be greater than those originally stated. For Aims 1c and 2, if the PI or IRB suspects that an unusual number of adverse events are occurring, the PI will determine if the adverse events occur significantly more frequently in any one condition. In the unlikely event of such analyses, the IRB will be informed of these results in a timely manner. Moreover, the IRB will be informed within one working day of any temporary or permanent suspension of the protocol.

15.0 Data and if applicable, Specimen Banking:

All data is kept in encrypted and password protected files on a locked Northwestern University network. Participant names and all other identifying information are kept in a separate, locked and protected location. Data will be stored for a period of five years after the study results have been published. At this point any paper-based data will be shredded and electronic data will be deleted. Data will not be stored for future use nor will data be stored outside of Northwestern. Data may be released to a third party if required by law (e.g., court order). All data will be kept in encrypted and password protected files on a locked Northwestern University network. Participant names and all other identifying information are kept in separate, locked and protected locations to ensure participant identity cannot be linked to their study data.

16.0 Qualifications to Conduct Research and Resources Available:

[name] will serve as the Northwestern site PI and [name] will serve as the study Co-Investigator.

Since her faculty appointment in 2013, [name] has received funding from the NCI and American Cancer Society to conduct research in cancer control and survivorship and health disparities in cancer outcomes. [name] is the leader of the Cancer Control and Survivorship Program and the director of the Cancer Survivorship Institute at the RHLCCC. He has received numerous grants to investigate cancer survivorship outcomes and disparities in patient-reported outcomes and culturally tailored interventions in oncology. Both [name] and [name] have numerous peer-reviewed publications in the area of cancer control and survivorship and ethnic minority health.

The research will be conducted within [name] laboratory space in the Department of Medical Social Sciences. [name] and her staff have computers, audio recorders for recording the interviews, and software for analyzing interviews (NVivo). [name] office and laboratory space also has locked filing cabinets for storing paper-based data.

We have not encountered serious psychiatric disturbance (e.g., suicidal ideation) in our previous psychosocial research in cancer. However, in the event we encounter participants in acute crisis during the interviews, we will provide immediate assistance in-person as appropriate and refer them for local treatment. Speaking privately with the participant, we will assess for suicidal

ideation, plan of action, and likelihood of carrying out the plan. We will help the participant obtain immediate assistance in the home (e.g., ask if spouse/friend can be contacted) and will encourage her to seek medical attention if she is at high risk. Local resource referrals will be kept on file to be used in the event of such an emergency. [name] is a licensed clinical health psychologist, experienced in psychotherapy, and counseling of patients and families dealing with chronic and acute medical conditions, particularly cancer. Drs. [name] and [name] have doctorates in clinical psychology and have provided individual therapy for patients through the supportive oncology program at the RHLCCC.

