PROTOCOL TITLE:

An e-Health Intervention to Improve Symptom Burden and Health-Related Quality of Life among Hispanic Women Completing Active Treatment for Breast Cancer

PRINCIPAL INVESTIGATOR:

[name].

Assistant Professor

Department of Medical Social Sciences

[name]

[name]

[contact]

VERSION DATE:

01/08/2018

1.0 Purpose of the Study:

This study aims to create and evaluate *Mi Guia* study aims, a culturally informed eHealth educational and psychosocial intervention for English or Spanish-speaking Hispanic women completing treatment for breast cancer. *Mi Guia* is grounded in evidence-based paradigms to improve our Primary Outcomes: Cancer-Related Symptom Burden and HRQOL and our Secondary Outcomes: cancer-specific distress, depressive symptoms, and markers of *Mi Guia* use. We propose a two-phase study to develop our Smartphone-based intervention that can be disseminated to survivors at a relatively low cost. We will use innovative methodology; MOST framework that will allow us to achieve both optimization and evaluation of *Mi Guia* by determining which single components or combination of components in *Mi Guia* affect our outcomes^{9,10}. Study components (one on breast cancer education, two psychosocial evidence-based components relevant to Hispanic women who have been diagnosed with breast cancer) will be paired with personal tele-coaching.

Aim 1 (Phase 1, Year 1): Create *Mi Guia*, an eHealth intervention designed to improve cancer-related symptom burden and HRQOL. Aim 1 is further broken down into four parts. Using a mixed-methods approach, we will 1a) collect qualitative data (n= 20) on the study content, 1b) conduct usability testing on the *Mi Guia* Smartphone application, and 1c) conduct feasibility testing (e.g., field trial) to refine the content in the components and the design of the Smartphone-delivered intervention for Hispanic women. Finally, we will add one more part to Aim 1, aim 1d) to conduct interviews with community stakeholders about the *Mi Guia/My Guide* application. These interviews with community stakeholders will not include any questions about participants. The interviews will only include questions about the application itself and their ideas on how to improve it.

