Aim 2 (Phase 2, Years 2 & 3): Optimize components for *Mi Guia* through an 6-week randomized trial to evaluate the efficacy of *Mi Guia* relative to a smartphone application on health education (*Mi Salud*), our control condition. The health promotion application, *Mi Salud*, includes health education content on nutrition, and general advice on lifestyle choices and prevention. Participants will complete the same procedures regardless of randomization assignment to help minimize potential confounding factors during the intervention or control delivery. Participants will be early-stage women completing active treatment (n= 90) We hypothesize that Hispanic BCS will find the smartphone application, *Mi Guia*, an acceptable and feasible way of accessing post-treatment relevant information. Furthermore, we expect that, in comparison to the control condition, *My Guide* will have a measurable, positive impact on this population's HRQOL and cancer-specific distress.

2.0 Background / Literature Review / Rationale for the study:

Ethnic minority and underserved populations are disproportionately burdened by cancer.¹ Among Hispanics, the largest and fastest growing ethnic minority group in the U.S., cancer is the leading cause of death whereas cardiovascular disease is the leading cause of death for African Americans and non-Hispanic Whites (NHWs). Hispanics also experience substantially lower rates of 5-year cancer-specific survival relative to non-Hispanic Whites (NHWs). Relative to NHWs, Hispanics are more likely to be diagnosed with advanced stages of breast cancer.² Furthermore, the average age of breast cancer diagnosis for Hispanics is 50 years, which is a decade earlier than for NHW women. Barriers to accessing and effectively engaging in health care, limited cancer information, beliefs about cancer are some factors that may contribute to these disparities.¹⁻³

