Aim 2 (Phase 2): Optimize components for Mi Guia through a 6-week randomized trial to evaluate the efficacy of Mi Guia relative to a smartphone application on health education (My Health), our control condition. Participants will complete the same procedures regardless of randomization assignment to help minimize potential confounding factors during the intervention or control delivery. Participants will be early-stage women completing active treatment (n= 90), see eligibility criteria above. A

minimum of 25 participants will meet the compromised cancer-related symptom burden and HRQOL. We hypothesize that Hispanic BCS will find the smartphone application, My Guide, an acceptable and feasible way of accessing post-treatment relevant information. Furthermore, we expect that, in comparison to the control condition, My Guide will have a measurable, positive impact on this population's HRQOL and cancer-specific distress.

Participants will be individually randomized, 1:1, to the health promotion application (control condition) or to the My Guide application (intervention condition). A longitudinal mixed effects linear model will be fit with the outcome (the Functional Assessment of Cancer Therapy-Breast; FACT-B) score as the dependent variable. Type of treatment (e.g., surgery type, hormonal therapy), time since completion of active treatment, stage of diagnosis, education, marital status, language, comorbidities and age at diagnosis will be examined for their associations with study outcomes for potential entry as covariates in the statistical model. Effect sizes will be calculated by dividing by the baseline standard deviation. The potential moderating effect will be examined by entering interaction terms into the model. Similar models will be fit to examine the subscales of the FACT-B. A total of 90 participants will be randomly assigned to one of 2 conditions (control or intervention), resulting in 45 participants per condition. The main effect of each intervention component will be evaluated by comparing the outcomes for participants who receive the intervention (n= 45) to those who did not receive the intervention (control; n=45), allowing a comparison of main effects. Participants will be compensated \$100 and reimbursed up to \$22 for travel and data usage.

Technology.

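### The two-arm Aim 2 trial can estimate only My Guide as a whole against My Health as a whole, so its 45 v 45 comparison is not a main effect of each component and the stated component objective cannot be met

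*Combined protocol and SAP*

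**What the plan says.** **The objective.** Section 1.0 (Purpose of the Study) adopts a "MOST framework that will allow us to achieve both optimization and evaluation of" the intervention. The same sentence says how this is to be done, namely by "determining which single components or combination of components in" the application have an effect. The section then lists the content: "one on breast cancer education, two psychosocial evidence-based components relevant to Hispanic women who have been diagnosed with breast cancer", all paired with tele-coaching. Aim 2 opens with "Optimize components for" Mi Guia in section 1.0, and section 4.0 (Specific Aim 2) repeats it: "Optimize components for Mi Guia through a 6-week randomized trial to evaluate the efficacy of Mi Guia".

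**The design.** Section 4.0 gives the allocation: "Participants will be individually randomized, 1:1, to the health promotion application (control condition) or to the My Guide application (intervention condition". The Trial Design text in the same section confirms the two conditions and says that procedures do not depend on assignment. Telecoaching follows one stepped-care rule, triggered by weekly use below 1.5 hours, in both conditions (Trial Design, and More on Weekly Telephone Coaching).

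**The analysis label.** Section 4.0 then states: "The main effect of each intervention component will be evaluated by comparing the outcomes for participants who receive the intervention" (n = 45) with those in the control condition (n = 45), "allowing a comparison of main effects".

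**The planned analyses.** Section 13.0 (Planned Analyses Aim 2) compares the two study conditions by ANCOVA and mixed models, on the outcomes and on the intervention targets. Planned Analyses Aim 1 is qualitative or descriptive. No section describes a factorial allocation, a randomised component or a component-level analysis.

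**The concern.** A main effect of a component can be estimated only if the design separates that component from the others, so that some participants have it and comparable participants do not while the rest of the package is held constant or balanced. Here, everything specific to My Guide goes to one arm together. The label in section 4.0 therefore names a quantity that the comparison does not estimate.

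What is at stake is the conclusion. If My Guide does better, the protocol's own words would let one whole-application difference be reported as an effect of the education component and of each psychosocial component. Section 1.0 would let the study be presented as having optimised the intervention, and section 2.0 calls the lack of knowledge about components a critical gap. A later team might keep or drop content on that basis without randomised evidence for doing so.

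**Working it through.** **Inputs.** Three content components: one education (E) and two psychosocial (P and Q) (section 1.0). Two arms of 45, allocated 1:1 to whole applications (section 4.0). The same coaching rule in both arms (section 4.0). Power of 80% for 0.63 SD with 40 per condition (section 13.0). No alpha is given with the power statement, so two-sided 5% is assumed.

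**1. The plan's own figure.** Normal approximation: power = Φ(d·√(n/2) − 1.96).
- n = 40: 0.63 × √20 = 2.817; 2.817 − 1.96 = 0.857; power 80.4%. The t-test gives 79.5%.
- n = 45: 0.63 × √22.5 = 2.988; 2.988 − 1.96 = 1.028; power 84.8%. The t-test gives 84.0%.
- A one-sided 5% t-test with 40 per arm gives 87.5%, which does not fit the stated 80%.

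The stated 80% is thus reproduced as the power of one contrast between two whole arms.

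**2. What the components would require.** Three components, each present or absent, make 2³ = 8 combinations. Besides the overall mean there are 8 − 1 = 7 effects: 3 main effects and 4 interactions (3 two-way, 1 three-way).

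**3. What two arms supply.** Code the columns as intercept, E, P, Q, and suppose first that My Health contains none of the three.
- My Guide row: (1, 1, 1, 1), 45 times.
- My Health row: (1, 0, 0, 0), 45 times.

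There are two distinct rows, so the rank is 2 of 4. The E, P and Q columns are identical and cannot be separated. With all interactions included, the rank is 2 of 8. One rank goes to the overall level, which leaves one contrast. That contrast is a combination of effects; none of the seven is individually estimable.

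**4. Does it depend on what My Health contains?** Section 10.0 says that control participants will learn more about breast cancer as well as healthy living, so some education content may be shared. If E is in both arms, the rows are (1, 1, 1, 1) and (1, 1, 0, 0). The rank is still 2.

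**5. Does it depend on sample size?** No. Repeating two rows 90, 900 or 9,000 times leaves the rank at 2.

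**6. What the one contrast is.** Let h be the effect of My Health's own content (nutrition, lifestyle and prevention; sections 1.0 and 4.0), and let s = 1 if the education component is shared and 0 if not. Then

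My Guide − My Health = (1 − s)·E + P + Q + interactions − h,

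plus any consequence of differing coaching uptake under the shared rule. As an illustration, take an observed difference of 0.63 SD with no interactions and no coaching difference:

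| s | h | E | P | Q | Difference |
|---|---|---|---|---|---|
| 0 | 0 | 0.63 | 0 | 0 | 0.63 |
| 0 | 0 | 0.21 | 0.21 | 0.21 | 0.63 |
| 0 | 0 | 0 | 0.315 | 0.315 | 0.63 |
| 0 | 0.21 | 0.28 | 0.28 | 0.28 | 3 × 0.28 − 0.21 = 0.63 |
| 1 | 0 | any value | 0.315 | 0.315 | 0.63 |

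The trial cannot tell these rows apart. The component values are invented for illustration; only 0.63 comes from the plan.

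**7. Coaching.** The rule is the same in both arms, so coaching is not a randomised factor. The calls a woman receives depend on her own use, so differences in calls arise after randomisation and do not identify a coaching effect.

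**The case against.** The strongest reply is that this is loose wording around a sound trial. The Aim 2 opening goes on to speak of the efficacy of Mi Guia against the control application. The hypotheses concern My Guide against control, section 13.0 compares conditions only, and the disputed sentence defines its own contrast as 45 against 45. No planned test or estimate is component-level. All of this stands, and it is why the remedy is a change of text. It does not remove the point: section 1.0 still states an objective, and section 4.0 still gives a result a name, that the design cannot support.

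One might also read components as the intervention targets or the FACT-B subscales. That could explain the sentence in section 4.0, but section 1.0 uses the word for content elements that affect the outcomes. Comparisons of targets and subscales remain effects of the whole application. The moderator interactions in section 4.0 are not specified as component terms. Usage is captured as measures such as logins and time, which are not randomised.

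It is also fair to say that main effect, used of study condition, is ordinary language where interaction terms are planned. Only its attachment to each component is wrong.

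Three stronger readings are tempting, and the documents do not support them:
- That the Aim 2 comparison is biased or underpowered. It is a valid randomised contrast, and its stated power reproduces.
- That the contrast equals the sum of the three components. My Health has content of its own and may share some breast cancer education.
- That both arms receive the same coaching. They share a rule; the calls received may differ.

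**Conclusion.** The point holds for the stated objective and the label. Of the 7 component-level effects that three components imply, the trial can estimate none individually. It yields one contrast, My Guide as a whole against My Health as a whole, at any sample size. An effect of coaching is not estimable by randomisation either.

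This rests on the allocation in section 4.0 and on the component count in section 1.0. It does not depend on whether My Health shares the education content. The power check assumes two-sided 5% and plays no part in the conclusion beyond showing that the plan's figure belongs to the whole-arm contrast.

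The ANCOVA, mixed models, comparisons of intervention targets and stated power are unaffected. The text should be corrected so that a whole-application difference is not reported as an effect of each component.

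**What to change.** 1. **Section 4.0, Specific Aim 2, analysis sentence.** Replace the opening with: *The effect of the My Guide application as a whole, compared with My Health, will be evaluated*. If the closing phrase on main effects is kept, make clear that it refers to study condition only.
2. **Aim 2 opening, sections 1.0 and 4.0.** Drop the reference to optimising components. Describe Aim 2 as a six-week randomised trial of the efficacy of Mi Guia as a whole relative to the control application.
3. **Section 1.0, MOST statement.** Delete both the claim that the framework will achieve optimisation in this study and the claim that the study will show which components or combinations affect the outcomes. Alternatively, state that component effects are outside this trial.
4. **Link to section 2.0.** Add a sentence saying that Aim 2 does not answer the component gap described there.

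Section 13.0 needs no change on this point. Sample size, randomisation, models and stated power stay as they are. The cost is that the sponsor gives up a component-level claim that the design cannot support.
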